Please note that the materials above were informed by the focus groups and individual interviews conducted among community members in the completed Phase I work. Specifically, participants preferred a fact-based approach that grabbed the attention from community members.

Data Management and Quality Assurance:

We will use the same coordination and communication procedures successfully utilized in our previous work including a weekly study team meeting held via teleconference. [name] and Mayo Clinic study staff provided training to the research coordinator on the study protocol on-site in Bethel.

All original participant forms are maintained in a locked file at the Healthy Pregnancies YKHC office. These forms with the exception of enrollment forms contain a study ID number only (e.g., no names or other identifying information). YKHC and Mayo Clinic study staff share the workload for assessments. For some period of time, a YKHC research coordinator was not hired and thus the program managers overseeing the project requested Mayo research staff to assist. The study staff from Mayo Clinic were added to the consent form as personnel modifications approved by the YKHC HSC as well as Mayo Clinic and Alaska Area IRB. The consent form allows for data sharing between Mayo Clinic and YKHC. An electronic data-tracking sheet with names and contact information is shared between Mayo and YKHC using a secure, encrypted email transfer.

When assessments are completed by YKHC, electronic (scanned) copies are transferred to Mayo Clinic Division of Biostatistics via secure encrypted email and stored on a secure server. Mayo Clinic staff enters data

into a secure REDCap (Research Electronic Data Capture) database that contains only the Study ID. Access to the information is restricted to the study statistician, [name], and study staff only. We will monitor quality control of the data through review of participant forms and procedures on-site in Bethel. Moreover, the biostatistician, [name], will perform monthly data checks and will also analyze the data. At both YKHC and Mayo Clinic, standard data security and monitoring procedures are in place. From the daily Native Sisters checklist, an implementation index has been created to permit exploration of dose response effects.

Program Evaluation:

For intervention villages, we will assess the pregnant woman's reported exposure to the social marketing campaign using continuous scales adapted from prior research. For example, her awareness/recall of the campaign messages and media (e.g., point of purchase displays), if she used/read various campaign media such as brochures and viewed the digital stories DVD, and if she shared these materials and/or the information with others in her village. An intervention exposure index will be created based on item responses to permit exploration of dose response effects.

De-identified data will be obtained from the YKDRH on the total number of positive pregnancy tests in each randomized village during the recruitment period. The study staff will track recruitment data, completion of each follow-up assessment among enrolled participants and use of NRT/other treatments.

To inform dissemination efforts, we will track and summarize the cost of intervention components including time spent by the Native Sisters and program materials displayed/distributed in each village. We will exclude development costs, as these would not be considered in disseminating the intervention.

Dissemination Plan To communicate and introduce the study to the local community we submitted a story to the region-specific "Tundra Drums" newspaper and locally owned radio stations (KYKD, KYUK). Dissemination of the results will occur after each phase of the project with guidance from our CAC. The first level of dissemination will be to the YKHC Human Studies Committee and Board. After receiving approvals, the second level of dissemination will be to the local community by submitting a story to local newspapers, locally owned radio stations, and the YKHC employee website. A booklet or brochure and a power point presentation with key project findings will be developed and approved by the YKHC. Presentations will be given to community members at local gatherings in Bethel and to YKDRH providers. The YKHC staff will also travel to the study villages to provide promotional items from the campaign, along with the brochures and DVD digital stories. They will meet with village councils to share results as feasible.

As the third level of dissemination, we will communicate the findings state-wide with our partners at the Alaska Native Tribal Health Consortium (ANTHC). The YKHC PR department will contract with businesses of their choice to develop three 30-second DVD video spots to be used in waiting areas of prenatal clinics in the Y-K Delta Region and the 15 health care regions served by the ANTHC. Information will also be included in ANTHC newsletters. The investigators and community partners will jointly present at the Alaska Native Health Research Conference held biannually with the audience comprising community members and researchers. Tangible products will be distributed such as intervention manuals and the digital stories DVD, and training will be made available elsewhere in Alaska.

A fourth level of dissemination will be to communicate the findings to national audiences. Mayo Clinic and community partners will jointly present at the Society for Research on Nicotine and Tobacco and other national scientific meetings. Also, we will communicate findings to our national AI/AN partners through our NCI funded U54 Community Networks Program grant ([name], PI) of which [name] is the research director.

The final level of dissemination will involve peer-reviewed publications written and co-authored with our community partner. As in prior studies, CAC members will also have the opportunity to co-author manuscripts and presentations. Utilizing these various venues for communication and dissemination of the project findings will maximize dissemination of the knowledge gained in this project. There should be lessons learned that will generalize to underserved populations as well as differences that will limit generalizability.

Check all that apply. If none apply, leave blank:

This is a multisite study involving Mayo Clinic and non-Mayo Clinic sites.

When checked, describe the research procedures/activities being conducted **only** at Mayo Clinic:

Mayo Clinic staff will be engaged in research activity at a non-Mayo Clinic site. *When checked, provide the location and a detailed description of the Mayo Clinic research staff involvement.*

The study will be conducted at the Yukon-Kuskokwim (Y-K) Delta Regional Hospital, Nicotine Control and Research Program, in Bethel, Alaska. The Yukon-Kuskokwim Health Corporation (YKHC) through the Indian Health Service P.L. 93-638 operates the Yukon-Kuskokwim Delta Regional Hospital. YKHC staff at the Y-K Delta Regional Hospital and Mayo Clinic staff share the workload of recruitment, conducting participant assessments in in the past conducted some of the intervention calls as a back-up to the YKHC research coordinator as well as the Native Sisters. Personnel modifications were approved by the YKHC HSC and Alaska Area and Mayo Clinic IRBs.

Mayo Clinic staff ([name]) traveled to Bethel, Alaska to train the research coordinator on the data collection and other study procedures. [name] is a clinical trials coordinator and study assistant at Mayo Clinic. We used the same coordination, communication and quality control procedures successfully utilized in our previous work. For ongoing trials in Alaska, we hold weekly conference calls with study staff in Bethel and at Mayo Clinic to discuss progress and problem solve issues related to recruitment and data collection. We also monitor quality control of the data on site in Bethel through review of participant forms and procedures every 3 months. [name], Biostatistician on this protocol will oversee the transfer of data forms and data storage.

The Mayo Clinic study assistant trained the research coordinator on-site in Bethel on focus group and individual interview techniques and ensure the coordinator met training requirements prior to recruitment for the focus groups.

This study is to establish and/or maintain an ongoing database or registry for research purposes only.

The research involves contact or interaction with subjects, for example, surveys, questionnaires, observation, blood draw.

The study involves audiotaping or videotaping

Data Confidentiality, HIPAA Subject Identifiers

Review the list of subject identifiers below and, if applicable, check the box next to each subject identifier being recorded at the time you are collecting/abstracting data/specimens for use in this study.

Subject Identifiers: Individually identifiable information, including demographic data, that identifies the individual or for which there is reasonable basis to believe it can be used to identify the individual. NOTE: Identifiers apply to subjects enrolled in your study and to the subject's relatives, household members, employers, etc.

Internal refers to subject identifiers that will be included in the dataset maintained by the study team.

External refers to subject identifiers that will be shared with persons outside of the immediate study team, for example, sent to an external collaborator or shared with a national registry.

SUBJECT IDENTIFIERS Check all that apply	INTERNAL IDENTIFIER	EXTERNAL IDENTIFIER
Name	X	
Social Security number		
Medical record/patient registration number, lab accession, specimen or radiologic image number		
Study number, subject ID, or any other unique identifying number, characteristic or code that can be used to link the identity of the subject to the data	X	
Dates: All elements of dates [month, day, and year] directly related to an individual. Their birth date, date of death, date of diagnosis, etc. Note: Recording a year only is not a unique identifier.	X	
Medical device identifiers and serial numbers		
Biometric identifiers, including finger and voice prints, full face photographic images and any comparable images		
Web Universal Resource Locators (URLs), Internet Protocol (IP) address numbers, email address	X	
Street address, city, county, precinct, zip code, and their equivalent geocodes	X	
Phone or fax numbers	X	
Account, member, certificate or professional license numbers, health beneficiary numbers		
Vehicle identifiers and serial numbers, including license plate numbers		
If None of the above identifiers will be recorded or maintained in the dataset and/or sent outside of the study team, please check "None".	 None	 None

Statistical Information

Note: Power analyses and study endpoints are not needed for a pilot or feasibility studies.

No statistical information. *If checked, please explain:*

Statistical Considerations

Phase I:

Sampling Strategy:

We used a stratified purposeful sample with divisions based on audience segment (pregnant women, family members, Elders), gender and current tobacco use status (Table 1). We stratified by gender because we found this approach facilitates interaction and participation. Among pregnant women, we held separate groups based on whether or not tobacco was used in the 3 months before pregnancy, as different messages were created targeting prevention and cessation of tobacco, respectively. Once data saturation (no new information is being collected) was achieved, the focus groups ceased. Between 6-12 participants per focus group is recommended. Based on our experience, focus groups of about 8 participants are ideal for information sharing and individual participation in this region. However, it was not feasible to recruit large numbers of Elders for focus groups, it was difficult to recruit non-users, and we experience scheduling difficulties. This lead to some focus groups being less than optimal and we conducted individual interviews when needed. We estimated 8 per focus group with pregnant women (N=32) and family members (N=32), and 4 per group with Elders (N=16); for a total of 80 participants. We had 23 pregnant women, 26 family members and 11 Elders that participated in focus groups/individual interviews.

For the second round of assessments, we recruited a different sample to pre-test draft concepts of the campaign messages and media. Based on sample size recommendations for qualitative interviews, we planned to conduct a total of 50 individual interviews (20 pregnant women, 20 family members and 10 Elders), with divisions based on the subsets in Table 1. For this second assessment, we interviewed 20 pregnant women, 21 family members and 11 Elders.

Data Analysis Plan:

Focus Group Qualitative Analysis. Sample characteristics were summarized using descriptive statistics. Audiotapes were fully transcribed with statements in Yupik translated locally. Focus group data were analyzed using content analysis and NVivo 10 to facilitate and streamline our analysis. Codes and categories were developed around the phenomena of interest. Initially these codes were based on the themes in our moderator guide; these themes have been refined and revised to incorporate themes that emerge from the data. In addition to open coding, planned comparisons across categories of interest were carried out (e.g., tobacco use status, gender), and connections established between identified categories. The analysis process was enhanced through memo writing and summarizing of emerging themes by the facilitators after each focus group. Focus group themes were discussed and refined with the facilitators until consensus is reached, and will be reviewed with our CAC. The analysis process was documented and outlined via the use of data management software, NVivo 10. Next qualitative findings will be synthesized with our health communications framework and relevant literature.

Individual Interviews Data Analysis: Data was analyzed using frequencies and other descriptive statistics for the overall sample. Trends within and between subgroups (e.g., pregnant women who use vs. do not use tobacco) were examined using the Chi-square (exact) or two-sample rank sum test. The investigative team synthesized the findings with our health communication framework and the literature. Results and recommendations were reviewed and finalized with our CAC, Northwest Strategies and nDigiDreams.

Phase II:

Power Statement:

Sample size calculations are based on the primary endpoint of tobacco use at 6 months postpartum. From our pilot data, of the 400 women who reported tobacco use during the 3 months prior to pregnancy, 83% reported tobacco use during the prenatal period and 69% at 6 weeks postpartum. Among the 17% of women

who quit tobacco use during pregnancy, the relapse rate was 63% at 6 weeks postpartum. Of the 432 women reporting no tobacco use in the three months before pregnancy, 75% reported tobacco use during the prenatal period, and 70% at 6 weeks postpartum. Alaska PRAMS data indicate similar cessation rates during pregnancy (20%) and rates of relapse postpartum (57%) in the southwest region. During the time periods these estimates were obtained, women received the same standard of care as in the proposed study. Therefore, we do not expect our usual care condition to impact tobacco use beyond the natural history of tobacco use in pregnancy. The Clinical Practice Guideline meta-analysis found that behavioral/psychosocial interventions for pregnant smokers were associated with an abstinence rate of 13% in late pregnancy vs. 7% for control conditions (OR= 1.8, 95% CI 1.5-2.3). We do not have guidance from the literature on the possible impact of interventions for baseline non-tobacco users but would expect greater impact in this group compared to those already using tobacco. Accordingly, we estimate the rate of tobacco use at 6 months postpartum to be 70% in our control villages and 55% in the intervention villages (estimated odds ratio 1.91) and in late pregnancy to be 80% vs. 65% with an odds ratio of 2.15. A difference of 15% would be of clinical significance in terms of the potential to impact the current standard of care at the YKDRH.

Estimates of intra-class correlations (ICC) within communities are quite modest, e.g., ranging from 0.002 to 0.012 for a variety of survey variables included in the Minnesota Heart Health Program. For the proportion currently smoking the estimated ICC was 0.00272. Other literature indicates that in community based trials using group-randomized designs (e.g., NCI Working Well Trial) the ICC ranged from 0.01-0.03 for the four outcome variables at baseline. Lumley et al. reviewed 9 cluster randomized trials of prenatal cessation interventions but most did not report the ICC and/or account for the clustering effect in the analysis. Table 3 (below) provides power estimates for the estimated outcomes with 16 villages total, average village participant size of 20 (total sample size = 320), and with varying ICC estimates. With an ICC of 0.01 we will have >80% power to detect the hypothesized differences between conditions at 6 months postpartum.

Table 3. Power estimates for 1-sided alpha=0.05 test

ICC	Hypothesized difference in tobacco use rates	
	Late Pregnancy 65 vs. 80%	6 Months Postpartum 55 vs. 70%
0	91	87
0.001	91	86
.01	86	81
.02	82	76
.03	77	71

Data Analysis Plan:

Analyses will be performed by [name], M.S. who has extensive experience in analysis of randomized clinical

trials, with consultation from [name]. Recruitment data will be summarized, including the total number of potential participants screened from each village, the number excluded for each of the specific inclusion/exclusion criteria, and the number of eligible women who agree to participate. To assess reach of the program in each village, we will calculate the proportion of subjects enrolled to total eligible subjects. We will compare the recruitment rates between control and intervention villages using the chi-square test. Potential village effects on recruitment rate will be explored.

Baseline demographics will be summarized and compared between intervention and control villages using the chi-square test for categorical variables and the two-sample t-test/rank sum test for continuous variables. The biochemically confirmed 7-day point prevalence tobacco use rate at 6 months postpartum will be summarized for each condition (point estimate and 95% CI) among participants eligible for follow-up (i.e., excluding women experiencing a miscarriage, abortion or fetal demise) and compared between conditions using generalized estimating equations (GEE) with a logit link function to account for clustering of outcomes within village (ICC) (**Aim 1**). We will utilize an intent-to-treat approach, with participants eligible but lost to follow-

up or who do not provide biochemical confirmation classified as using tobacco. The analysis will be supplemented with multiple imputation methods to classify lost to follow-up as tobacco users or non-users. GEE will also be used to examine condition differences on the point prevalence tobacco use rates at 12 weeks/week 36 gestation, and at 8 weeks postpartum. Because only 14 df are available for the test of the intervention we will employ a small sample correction to the standard GEE. For these analyses, the stratification factor (village size) will be adjusted for in the analysis. Based on the biochemically confirmed tobacco use status at baseline, in an exploratory fashion we will examine potential treatment effects separately among baseline non-tobacco users and tobacco users respectively using GEE. Within intervention villages only, exposure dose will be tested as a predictor of tobacco use at 36 weeks gestation and 6 months postpartum using GEE. A similar analysis will be performed using the intervention implementation index to examine potential dose response effects. Assuming an ICC of 0.01 and an effective sample size of 135 subjects in the intervention arm after correction for the ICC, there will be 80% power to detect an effect size of at least 0.5 standard deviation units when examining the association of intervention exposure (i.e., continuous measure) and abstinence rates. Potential village differences on intervention exposure or implementation will be summarized graphically and compared using GEE. The percentage of enrolled participants who complete 6- month follow-up postpartum (retention) will be compared between intervention and control villages using GEE.

We will follow procedures suggested by MacKinnon to assess mediation (**Aim 2**), fitting three GEE models to the data. We will first estimate the intervention effect separately for the dependent variable (with regression adjustment for covariates). That model provides an estimate of the total effect of the intervention, which MacKinnon labels C. Next we will estimate the intervention effect for each mediator (with regression adjustment for covariates); that model provides an estimate of the effect of the intervention on the mediator, which MacKinnon labels A. Finally we will estimate the mediated intervention effect for the dependent variable by adjusting for the mediator (and covariates); that model provides an estimate of the unmediated (i.e., direct) intervention effect, which MacKinnon labels C, and the intervention-adjusted effect of the mediator on the dependent variable, which MacKinnon labels B. Assuming an ICC of 0.01 and an effective sample size of 270 subjects after correction for the ICC, there will be 80% power to detect an effect size of at least 0.35 standard deviation units for paths A and B assuming a two-sided, alpha=0.05 test at 6-months postpartum.

Treatment condition differences on changes in other variables targeted (see Table 4) will be examined using GEE with a logit (binomial outcome) or identify (continuous outcome) links as appropriate.

We will summarize the cost of the program per pregnant woman enrolled (reached) along with cost per woman abstinent from tobacco at 6 months postpartum follow-up using descriptive statistics.

Endpoints

Primary:

Biochemically confirmed tobacco abstinence at 6-months post-partum.

Secondary:

Biochemically confirmed tobacco abstinence at end of pregnancy. Also, changes in proposed theory-based mediators of intervention efficacy.

Project Timeline

We have received approval from NIH to extend out the study timeline from 5 to 6 years total. We are currently beginning the 5th year of our 6-year NIH grant. Table 4 shows the timeline for the remaining Phase II

activities. We will request from NIH a 7th project year as a no-cost extension to complete analyses and dissemination if necessary and long as remaining funds permit.

Table 4

PROJECT TIMELINE, YEARS 3-7,
Dates: May 1, 2015 – April 30, 2020

Activity	Year 3 2015-2016				Year 4 2016-2017				Year 5 2017-2018				Year 6 2018-2019				Year 7 2019-2020 No Cost Extension					
	Month:	1-3 May -Jul	4-6 Aug -Oct	7-9 Nov -Jan	10- 12 Feb -Apr	37- 39 May -Jul	40- 42 Aug -Oct	43- 45 Nov -Jan	46- 48 Feb -Apr	13- 15 May -Jul	16- 18 Aug -Oct	19- 21 Nov -Jan	22- 24 Feb -Apr	25- 27 May -Jul	28- 30 Aug -Oct	31- 33 Nov -Jan	34- 36 Feb -Apr	37- 39 May -Jul	40- 42 Aug -Oct	43- 45 Nov -Jan	46- 48 Feb -Apr	
Phase I																						
Manuscripts/scientific presentations of results; tribal approval						X																
Phase 1 results submitted to journal							X	X														
Phase II																						
Hire and train Native Sisters		X	X	X																		
IRB/Tribal submission of Phase 2 working protocol	X	X																				
Train Health Aides in study villages			X	X																		
Mass produce media/materials after tribal approvals		X																				
Recruitment			X	X	X	X	X	X	X	X	X	X	X									
Intervention delivery			X	X	X	X	X	X	X	X	X	X	X	X	X	X	X					
Follow-up				X	X	X	X	X	X	X	X	X	X	X	X	X	X	X				
Analysis							X								X	X	X	X	X	X	X	
Scientific and community dissemination (Phase II)																				X	X

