To create the digital storytelling DVD, two workshops were held in Bethel, Alaska in January and February of 2015 and conducted by nDigidreams, Inc. The target sample was 10 participants (5 each workshop). A total of 12 people participated (3 males, 9 females). Of these, 9 were community members and 3 were health care professionals. Six of the stories were translated into Yupik. In addition, Northwest Strategies finalized and mass produced all other campaign material including posters, brochures, and promotional items.

Community and Study Setting

The community, Alaska Native people of Yupik or Cupik ethnicity residing in the Y-K Delta region (population 25,000), is fairly homogeneous with respect to culture and language with most residents fluent in both English and Yupik. The population is of low SES and most maintain a subsistence lifestyle. Bethel (population 6,000) is the hub for the 56 villages of this region (population 28-1,133). No road connects the villages and residents travel by small plane, boat or snow machine. A typical village has a combined elementary and secondary school, a local village council, health clinic, store, post office, church and community center. The Y-K Delta Regional Hospital (YKDRH), owned and operated by the Yukon-Kuskokwim Health Corporation (YKHC), is located in Bethel and provides health care for residents. The YKDRH employs 170 Alaska Native health aides who work in their home villages, with 1-8 per village based on its size. Prenatal care visits are scheduled at the YKDRH (96% of women receive prenatal care) including a visit at week 36 gestation. At this time, high-risk pregnancies are triaged for delivery at the Alaska Native Medical Center in Anchorage and women from the villages reside at the Bethel pre-maternal home until delivery. There is an average of over 600 births each year. A scheduled visit at 8 weeks postpartum is attended by 70% of women. As part of normal care, prenatal, obstetrical, and WIC providers routinely ask about tobacco use and provide brief advice to quit but more substantive cessation interventions are not provided. Less than 2% of pregnant women enroll each year in the YKDRH clinical cessation program.

CBPR Approach

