In Phase II, we will conduct an evaluation of the intervention applying a group-randomized design with village as the unit of assignment. Sixteen villages were selected and randomly assigned to receive the intervention (8 villages) or control condition (8 villages) with ≥ 22 pregnant women recruited per village.

Subject population:

Sample size calculation. We estimate recruiting ≥ 22 pregnant women per village (N=352). Accounting for an estimated attrition rate of 10% due to miscarriage, abortion or fetal demise, we plan to achieve a final sample of at least 320 women eligible for follow-up. All pregnant women (tobacco users and non-users) will be eligible for enrollment.

Actual accrual. We met our targeted sample size of 352 women enrolled. Encouragingly, overall participation from control villages (n=164) was similar to overall participation from intervention villages (n=188). Although we estimated 22 or more women enrolled in each village, this was not feasible. Study villages were more or less interested in participating, with a range of 2 to 42 women enrolled in the 16 study villages.

Inclusion Criteria:

Participants consist of 352 Alaska Native pregnant adults age 18 and older. To be eligible for the study, Alaska Native pregnant women participants must:

- Be 18 years of age or older
- Provide written informed consent
- Currently 36 weeks or less gestation
- Access to a working telephone

Exclusion Criteria:

Individuals will be considered ineligible to participate in the study if they are:

- Not Alaska Native
- Under the age of 18
- Currently not pregnant or ≥ 37 weeks gestation
- No access to a working telephone
- Refuse to provide written informed consent

Will a Certificate of Confidentiality be obtained? If yes, provide an explanation.

No, a Certificate of Confidentiality will not be obtained.

Study Design

Methods: *Describe, in detail, the research activities that will be conducted under this protocol:*

Phase IA. Social Marketing Campaign Development

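### The >80% power claim at 6 months postpartum makes no visible allowance for counting lost or unconfirmed women as tobacco users

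*Combined protocol and SAP*

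**What the plan says.** The Power Statement (Statistical Considerations, Phase II) cites pilot data on reported use at 6 weeks postpartum: 69% of 400 women who used tobacco before pregnancy and 70% of 432 who did not. After also citing regional surveillance figures and a guideline meta-analysis, it states that "we estimate the rate of tobacco use at 6 months postpartum to be 70% in our control villages and 55% in the intervention villages". Aim 1 gives the same pair as its hypothesis for the biochemically confirmed rate.

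The table is headed "Table 3. Power estimates for 1-sided alpha=0.05 test" and assumes an "average village participant size of 20 (total sample size = 320), and with varying ICC estimates". The conclusion drawn is "With an ICC of 0.01 we will have >80% power to detect the hypothesized differences between conditions at 6 months postpartum"; the Table 3 cell is 81.

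The Phase II sample size paragraph goes from 352 enrolled to at least 320 eligible for follow-up: "Accounting for an estimated attrition rate of 10% due to miscarriage, abortion or fetal demise". The Phase II Data Analysis Plan excludes women with these pregnancy losses from the primary comparison. Of eligible women it says that those lost to follow-up are treated in the same way as those without confirmation: "up or who do not provide biochemical confirmation classified as using tobacco". Multiple imputation is planned as a supplement. The primary endpoint is confirmed abstinence at 6 months postpartum.

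**The concern.** The rule that missing means user moves both arms towards 100% use and shrinks the difference between them. A power calculation for this analysis needs the rates as they will be analysed, after the rule has been applied. The 70% is almost exactly the pilot rate of reported use, with no visible adjustment for confirmation or loss. The 10% allowance covers only women who leave the analysis set, so nothing is set aside for loss to follow-up or unreturned saliva among the 320 who remain.

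The plan does not expect complete follow-up. It specifies imputation for women lost and a comparison of 6-month retention between arms. Under Procedures, the week 26 postpartum assessment is not among the in-person Bethel visits; it is done by phone, with provision for returning saliva by mail.

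At stake is how the result is read. Recruitment is complete, so the sample cannot absorb a shortfall. A null result would be judged against power of more than 80%, which has very little margin.

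**Working it through.** **Inputs.** 70% vs 55%, one-sided alpha 0.05, 16 villages averaging 20 women, ICC 0.01 (Power Statement and Table 3). Villages were "randomly assigned to receive the intervention (8 villages) or control condition (8 villages"), so there are 8 × 20 = 160 women per arm.

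**1. Reproduce Table 3.** Design effect = 1 + (20 − 1) × 0.01 = 1.19. Effective n per arm = 160 / 1.19 = 134.5. For a two-proportion normal test, power = Φ[(d − 1.645 × SE0) / SE1], where SE0 uses the pooled rate and SE1 the separate rates. With d = 0.15:

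- SE0 = √(2 × 0.625 × 0.375 / 134.5) = 0.0590
- SE1 = √((0.70 × 0.30 + 0.55 × 0.45) / 134.5) = 0.0583
- power = Φ(0.907) = 81.8%, against the stated 81

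The other 6-month cells give 87.3, 86.7, 76.5 and 71.7 (stated 87, 86, 76, 71). The late-pregnancy cells also agree to within about a point. The arithmetic of Table 3 is sound.

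**2. Source of the 70%.** Pooled pilot rate = (400 × 0.69 + 432 × 0.70) / 832 = 69.5%.

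**3. Apply the rule.** Let L be the share of abstinent women in each arm who are lost or unconfirmed at 6 months. Only these women change category: a woman who reports use needs no cotinine test, and a lost user is still counted as a user. The analysed rate is p + (1 − p)L, so the analysed difference is 0.15(1 − L). The documents give no L. The values below are assumed and equal in both arms, with the power formula of step 1.

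| L | Control | Intervention | Difference (points) | Power |
|---|---|---|---|---|
| 0 | 70.0% | 55.0% | 15.0 | 81.8% |
| 5% | 71.5% | 57.25% | 14.25 | 78.9% |
| 10% | 73.0% | 59.5% | 13.5 | 75.9% |
| 20% | 76.0% | 64.0% | 12.0 | 69.4% |
| 30% | 79.0% | 68.5% | 10.5 | 62.3% |

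Power crosses 80% at about L = 3%.

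**4. The other reading.** Suppose 70% and 55% already include the rule, with the same share L of all eligible women missing. The rate among women with data is then (p − L) / (1 − L):

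- L = 10%: 66.7% vs 50.0%, a difference of 16.7 points
- L = 20%: 62.5% vs 43.8%, a difference of 18.8 points (62.5 − 43.75)

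On this reading Table 3 stands, but the effect it assumes among women with data is larger than 15 points.

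**The case against.** The strongest reply is that Table 3 contains no error and that the documents call 70% and 55% 6-month rates, used in Aim 1 for the confirmed endpoint. Formally they are assumed endpoint rates, and the 55% is not a pilot figure at all. This stands. A reader might infer that 6-week self-reported rates among women with data were entered unchanged. The documents do not say so, nor how missing pilot reports were handled. What remains is that the plan does not say whether the pair is before or after the rule, and that reading it as after requires an effect the documents do not support.

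A reader might also infer that the 15 points survive only if every eligible woman is reached and returns saliva. That is too strong, because only lost or unconfirmed abstainers dilute the difference. If loss falls mainly on users, the dilution is smaller than overall loss suggests.

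It is tempting to take the Community and Study Setting statement, "A scheduled visit at 8 weeks postpartum is attended by 70% of women", as evidence of 30% loss. It describes routine clinic attendance, no saliva is scheduled at week 8, and missed in-person assessments are done by phone. It is not a study loss rate.

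Nor do 6-week timing and self-report reduce power by themselves: with the 15 points kept, 80% vs 65% gives 87.0% at the same ICC. The nondisclosure remark in Procedures concerns pregnancy and carries no rate.

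Finally, the planned confidence intervals, imputation and retention comparison will help in reading a null result. They do not correct the stated power.

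**Conclusion.** The concern holds as a gap in the inputs to the power statement, not as an arithmetic error. At ICC 0.01 with 320 women, one-sided power is about 82% with no loss among abstainers, and about 79%, 76%, 69% and 62% at L = 5%, 10%, 20% and 30%. About 3% is enough to bring it below 80%.

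These figures rest on three assumptions: 70% and 55% are true rates before the rule, L is equal in both arms, and the normal approximation behind Table 3 applies. Unequal loss could widen or narrow the difference. Because no loss rate is documented, it cannot be said that the trial has less than 80% power, only that the claim depends on an unstated condition with little margin. Whether the test should be one-sided is a separate matter. Using 317 women (352 × 0.9) in place of 320 makes a negligible difference.

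**What to change.** In the Power Statement:

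- state the share of eligible women expected to be lost or unconfirmed at 6 months, and the basis for it;
- say whether 70% and 55% are before or after lost and unconfirmed women are classed as users;
- restate Table 3 with the analysed rates and power at L = 10%, 20% and 30%, noting the assumption of equal loss;
- qualify the claim of more than 80% power accordingly.

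The cost is a recomputed table and a few sentences. No more women and no change to the analysis are needed. The downside is a less favourable stated power.
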